6. SPECIFICATION OF OUTCOME

The primary outcome KOOS QoL subscale and all secondary outcomes will be analysed as the ITT set. Secondary analyses will be performed as PP set for the primary outcome and the remaining 4 KOOS subscales: Pain, Symptoms, Activity of daily living and Sports and recreation.

6.1. Primary outcome:

The primary outcome of the study is the difference between the two treatments as mean change of the KOOS QoL subscore from baseline to the two-years follow-up.

6.2. Secondary outcomes:

The difference between the two treatments in the following outcomes:

1. The mean change in the **KOOS Symptoms** subscore from baseline till two years.
2. The mean change in the **KOOS Pain** subscore from baseline till two years.
3. The mean change in the **KOOS Activities of Daily Living** subscore from baseline till two years.
4. The mean change in the **KOOS Sports and Recreation** subscore from baseline till two years.
5. The mean change in the **IKDC 2000 subjective score** from baseline till two years.
6. Knee laxity as measured by the **Lachman's test** at two years.
7. Knee laxity as measured by the **Pivot shift test** at two years.
8. Knee laxity as measured by the **KT-1000** at two years.
9. Range of motion as measured by the mean **extension deficit** in the involved knee compared to the uninvolved knee at two years.
10. Range of motion as measured by the mean **flexion deficit** in the involved knee compared to the uninvolved knee at two years.
11. The **Tegner activity score** at two years.
12. The **Activity Scale level** at two years.
13. **Return to sports** at two years.
14. The mean change in the **One leg hop test** from baseline till two years.

15. The degree of degeneration in the involved and uninvolved knee, classified by the **Kellgren-Lawrence** classification system, at two years.
16. The number of **Adverse events** including bleeding, DVT, infection, donor site pain, arthrofibrosis or cyclops within two years after the operation.
17. The number of new **menisci injuries** at two years.
18. The number of new **cartilage injuries** at two years.
19. The number of **ACL graft re-ruptures** at two years.
20. The number of **Reoperations** within the two-years follow-up.

Secondary outcome derived from the primary outcome

21. The difference between the two treatments in **subjective treatment failures**, defined as KOOS QoL subscore < 44 point

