Menisci surgery including suturing, resection or transplantation.

Reoperations due to cartilage surgery.

Re-arthroscopy due to other reasons.

Revision surgery because of graft rupture, both first and second stage revision surgery.

8. SAMPLE SIZE CALCULATION:

The sample size was calculated as for a superiority study, based on the null hypothesis that quality of life following double-bundle ACL reconstruction is equal to KOOS quality of life following single-bundle ACL reconstruction.

The primary outcome, KOOS QoL subscale, was used for the sample size calculation. A minimal important change (MIC) in QoL of 8 points, has been considered sufficient [23]. With equal allocation in both arms, a standard deviation of 15 points, power of 80%, and assuming a two-sided significance-level of 0.05, the sample size was calculated to be 56 patients in each treatment group.

To allow for 5% drop-outs, the final sample size was set to be 60 patients in each treatment arm, and 120 patients in total.

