15. The **Kellgren-Lawrence classification** at two years will be analysed with the Wilcoxon-Mann-Whitney test for ordered 2xc tables [REF: Chapter 6 of Fagerland MW, Lydersen S, Laake P (2017) Statistical Analysis of Contingency Tables. Chapman & Hall/CRC, Boca Raton, FL.] A P-value for the null hypothesis that the two treatments have equal distributions across the categories will be presented.
16. **Adverse events:** the graft failures and new meniscus injuries will be analysed. The null hypothesis of equal probabilities will be analysed with a Fisher mid-P test [REF: Chapter 4 of Fagerland MW, Lydersen S, Laake P (2017) Statistical Analysis of Contingency Tables.

Chapman & Hall/CRC, Boca Raton, FL.] A P-value for the null hypothesis that the two treatments have equal distributions across the categories will be presented.

17. **Reoperations:** The null hypothesis of equal probabilities will be analysed with a Fisher mid-P test [REF: Chapter 4 of Fagerland MW, Lydersen S, Laake P (2017) Statistical Analysis of Contingency Tables. Chapman & Hall/CRC, Boca Raton, FL.]

Secondary outcome derived from the primary outcome

18. The difference between the probabilities of **treatment failures**, defined as KOOS QoL < 44 points, will be estimated and a 95% Newcombe hybrid score CI will be reported. The null hypothesis of equal probabilities will be analyzed with a Fisher mid-P test [REF: Chapter 4 of Fagerland MW, Lydersen S, Laake P (2017) Statistical Analysis of Contingency Tables. Chapman & Hall/CRC, Boca Raton, FL.]

10.3.3. Subgroup analysis:

A separate analysis of the primary outcome in the blinded versus not blinded patients will be performed. The subgroup would contain patients with randomization number 1-61 versus 62-120. The subgroup analysis will be performed by adding an interaction term between blinded and treatment and an interaction term between blinded and (treatment x time) to the linear mixed model. The P-values for these interaction terms will indicate whether any difference in treatment effects exists between blinded and not blinded patients.

10.3.4. Missing data analysis:

Recording of the reasons for missing data will be done.

The KOOS subscales, the IKDC 2000, and the one leg hop test will be analysed with linear mixed models. These models account for missing data on individual time points, thus obviating the need to impute missing values.

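### Graft failures, new meniscus injuries and reoperations get only a Fisher mid-P test, while the SAP's other binary outcomes also get a risk difference with a 95% Newcombe interval

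*SAP*

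**What the plan says.** Section 6.2 introduces all the secondary outcomes as "The difference between the two treatments in the following outcomes". Outcomes 17, 19 and 20 on that list are new meniscus injuries, ACL graft re-ruptures and reoperations.

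Section 10.3.2 then fixes the analyses:

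- Item 16, on adverse events, states that "the graft failures and new meniscus injuries will be analysed. The null hypothesis of equal probabilities will be analysed with a Fisher mid-P test". A P-value is to be presented.
- Item 17 (reoperations): the same test of equal probabilities, and nothing more.
- Items 13 (return to sports) and 18 (KOOS QoL below 44 points): the same test, but the difference between the treatment probabilities "will be estimated and a 95% Newcombe hybrid score CI will be reported".

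Section 10.1 promises counts and percentages by arm for categorical data. Section 11 lists the event categories and counts each patient once per category. It adds no between-arm estimate. In section 8 the trial is sized on KOOS QoL alone: "To allow for 5% drop-outs, the final sample size was set to be 60 patients in each treatment arm, and 120 patients in total".

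**The concern.** Section 6.2 defines the outcome as a difference, and section 10.3.2 never estimates it for these three harms. What is planned is a test of equality, whose P-value mixes the size of a difference with the amount of information. When events are few, a P-value above 0.05 is compatible both with similar risk and with a substantial excess in one arm, and only an interval tells these apart. The SAP already has a suitable interval and uses it for its other binary outcomes. Leaving it out here means that the excess risk the data cannot exclude is not pre-specified to be shown. The primary conclusion is not affected.

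**Working it through.** **Inputs.** From section 8: 60 per arm, 5% drop-out, two-sided alpha 0.05. The alpha is stated for the primary outcome and assumed here for the mid-P tests. Evaluable per arm: 60 x 0.95 = 57, so 57 and 60 bracket the analysis. Event rates are not in the SAP; all rates below are assumptions.

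**The plan's own figure.** With a difference of 8 points, SD 15 and 80% power, n = 2 x 15² x (1.960 + 0.842)² / 8² = 55.2, rounded up to 56 per arm, as stated. 56 / 0.95 = 58.9, so 59; the plan sets 60. The sample size reproduces, but it was chosen for a continuous score and not for event counts.

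**Two definitions of the two-sided mid-P.** The SAP names the test and cites a textbook chapter but does not write out the two-sided rule, so both usual versions were run:

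- A: two-sided Fisher P minus half the probability of the observed table.
- B: twice the one-sided mid-P.

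**Power.** All 2x2 tables with n per arm were enumerated. Each was marked as a rejection if mid-P < 0.05 and weighted by its binomial probability under the assumed rates. Power at n = 57 / n = 60:

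| Assumed rates | Definition A | Definition B |
|---|---|---|
| 5% v 10% (doubling) | 13% / 13% | 13% / 14% |
| 10% v 20% (doubling) | 27% / 28% | 30% / 32% |
| 15% v 30% (doubling) | 44% / 45% | 47% / 50% |
| 20% v 40% (doubling) | 60% / 63% | 64% / 67% |
| 5% v 15% (tripling) | 37% / 39% | 40% / 43% |
| 8% v 24% (tripling) | 61% / 63% | 65% / 67% |
| 10% v 30% (tripling) | 75% / 76% | 77% / 79% |

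With 3 events in one arm, the other arm needs 11 (definition A) or 10 (definition B) for P < 0.05, at 57 or 60 per arm.

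**Worked example, 3/60 v 9/60.** The observed table has conditional probability 0.0480, and the two-sided Fisher P is 0.1254.

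- Definition A: 0.1254 - 0.0480/2 = 0.101.
- Definition B: with equal arms each tail is 0.1254/2 = 0.0627, so 2 x (0.0627 - 0.0240) = 0.077.

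The Wilson 95% limits are 1.7% to 13.7% for 3/60 and 8.1% to 26.1% for 9/60. The Newcombe hybrid score limits for the difference of 0.150 - 0.050 = 0.100 are:

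- lower: 0.100 - √[(0.150 - 0.081)² + (0.137 - 0.050)²] = -0.011
- upper: 0.100 + √[(0.261 - 0.150)² + (0.050 - 0.017)²] = +0.216

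So P exceeds 0.05 under either definition, and an excess of more than 20 percentage points is not excluded. The same holds in kind for 3 v 6 events (difference +5.0 points, -5.2 to +15.7) and 6 v 12 events (+10.0 points, -3.0 to +22.9), each with 60 per arm.

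**The case against.** Four objections deserve an answer.

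1. A reader might infer that the P-value would be the only between-arm safety result. The SAP does not support that. Section 10.1 commits to counts and percentages by arm, and the flow chart has a place for graft failure in each arm. The difference is then a subtraction, and a reader could compute an interval. This stands, and it limits the point: what is missing is a pre-specified estimate with its uncertainty. Percentages by arm do not show precision.

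2. A reader might infer that the test would usually miss a doubling or a tripling. That depends on rates the SAP does not give. Of the rates tabulated, it holds for both only at 5%. A doubling is still missed more often than not at 10%, and at 15% apart from about even odds with 60 per arm under definition B. At 8% and above a tripling is more often detected than missed, and so is a doubling at 20%. Reoperations pool many causes, so a low rate cannot be presumed there.

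3. Low power for uncommon secondary events is ordinary in a trial sized for a patient-reported score, and an interval does not raise it. This stands. The power figures show why a P-value alone is uninformative; they are not a defect of items 16 and 17.

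4. Harms are not singled out: items 6, 7, 11, 12 and 15 also give only a P-value. Those outcomes are ordinal and have no single obvious contrast. The harms are binary per patient, like items 13 and 18, so that comparison stands. Nothing in the SAP says that P > 0.05 will be read as equal safety, and no such intention is alleged.

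**Conclusion.** The point holds as an inconsistency within the SAP that should be corrected. Outcomes defined in section 6.2 as differences are tested but not estimated in items 16 and 17, although the plan's own method for binary outcomes would do it. The mid-P value is the only planned inferential comparison of graft failures, new meniscus injuries and reoperations.

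The size of the problem rests on assumed event rates, two-sided alpha 0.05 and 57 to 60 evaluable patients per arm. At a lower rate of 5%, power is about 13-14% for a doubling and 37-43% for a tripling. It rises to 61-67% for 8% v 24% and 60-67% for 20% v 40%. In the example of 3/60 v 9/60, a mid-P of 0.08 to 0.10 goes with an interval reaching +21.6 percentage points.

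**What to change.** In items 16 and 17 of section 10.3.2, estimate the between-arm difference in the proportion of patients with at least one graft re-rupture, at least one new meniscus injury and at least one reoperation, each separately. Give each a 95% Newcombe hybrid score interval, as in items 13 and 18, and keep the Fisher mid-P test as a supplement. It would help to state which two-sided mid-P definition is used.

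The cost is a sentence in each item. The method is already specified in the plan, and no further data are needed. The downside is that the intervals will be wide and the safety statement more cautious. Power stays as it is.

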The patients were recruited from the outpatient clinic at Oslo University Hospital during the entire inclusion period. From March 1st, 2013 Martina Hansens Hospital was added as recruitment hospital. Initially, the interventions were performed at Oslo University Hospital. From March 1st, 2013 until end of inclusion, the site of intervention was changed to Martina Hansens Hospital. Both hospitals perform more than 100 ACL reconstructions yearly and recruit patients from a rural environment. A single surgeon performed the surgery at all study participants except two in both hospitals. The surgeon was experienced and instructed in how to perform the intervention, prior to inclusion of the first patient.

Collection of baseline information was conducted after a minimum of two months of rehabilitation and within three months before the operation. The 1 and the two-years follow-up, was performed within three weeks from the examination date. Patients responses obtained outside of these time frames will not be considered in the per protocol analysis. In the intention to treat (ITT) analysis all collected data at each time point will be considered. The average time until the examination was recorded in both groups for one and two years.

3.3. Inclusion and exclusion criteria:

Inclusion criteria:

The participants had to comply with the following at randomization:

- 1) Age from 18 to 40 years.
- 2) Symptoms from their knee due to a primary ACL injury
 - verified by history,
 - clinical assessments (Lachman >1+ and/or positive Pivot shift test)
 - and identified under surgery
- 3) Successfully completed a preoperatively 3 (minimum 2) months of ACL rehabilitation program supervised by a physiotherapist.

Exclusion criteria

- 1) A previous ACL reconstruction in the involved knee.
- 2) A subtotal (partial) ruptured ACL.
- 3) PCL, LCL or PLC injury.
- 4) Increased medial, lateral or posterolateral ligament laxity at the operating table, compared with the uninvolved leg.
- 5) ACL injury of the uninvolved knee.
- 6) Less than 50% of one of the menisci preserved after surgical treatment.
- 7) Established osteoarthritis (Kellgren-Lawrence classification grade 3 or 4) identified at the baseline standing front radiographs of the knee.
- 8) Hamstring tendons with insufficient graft thicknesses after preparation (defined as less than of 5.0 mm in diameter for the PL, and 6.0 mm for the AM bundle).

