9. RANDOMISATION/BLINDING

9.1. Randomisation

A nurse not involved in the research project performed a computer-generated block randomization, ten patients in each block. The allocation sequence was generated by a software program:

(<http://randomization.com>) and was conducted with a 1:1 ratio between the treatment arms. With 60 patients within each intervention group, twelve blocks of ten patients was needed. 120 sequentially numbered, opaque, sealed envelopes, containing a label describing one of the two interventions, were placed in the operating theatre at operation. The envelope was opened only if the patient fulfilled the inclusion criteria and the baseline assessments. One of the assisting nurses would open the envelopes at the request of the surgeon. The randomization was performed only after the ACL rupture was verified by arthroscopy, and at least 50 % of each menisci was left intact after surgical treatment, and if the hamstring graft sizes were sufficient after harvesting (the minimal desired hamstring graft sizes were 5.0 mm for the PL bundle and 6.0 mm in diameter for the AM bundle).

9.2. Level and method for blinding:

KOOS/IKDC and the activity scales: Initially, the trial participants were not intentionally blinded for the intervention, but the outcome assessor was blinded. The outcome assessor ensured that the PRO from the patients were complete.

The level of blinding was changed during the enrollment, and the study participants number 62 – 120 were consequently blinded for the intervention. Unblinding was performed after the assessments of the two-years follow-up.

Functional tests: The outcome assessor that completed the functional tests, was blinded for the intervention.

Clinical assessment: The clinical assessment was performed by the assisting, orthopaedic surgeon [name]. The surgeon was not blinded, as she was also present during the initial surgery.

Radiographic imaging: The radiologist was not blinded, as the intervention was visible at the radiographic imaging.

Data analysis: The statistical advisor will be blinded when performing the analysis.

10. STATISTICAL METHODS:

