10.3. STATISTICAL ANALYSIS

10.3.1. Primary outcome analysis:

The **KOOS QoL subscore** will be analyzed with a linear mixed model with treatment, time point (baseline, 1 year, 2 years), and treatment x time point interaction as fixed effects. A random intercept will be used. Based on the fitted model, we will estimate the mean baseline, 1 year, and 2 years values (with 95% CIs) for each treatment, and the between-treatment difference in changes from baseline to 2 years (with 95% CI and a P-value for the null hypothesis of no difference).

10.3.2. Secondary outcomes analysis:

1. The **KOOS Symptoms** subscore will be analyzed with a linear mixed model with treatment, time point (baseline, 1 year, 2 years), and treatment x time point interaction as fixed effects. A random intercept will be used. Based on the fitted model, we will estimate the mean baseline, 1 year, and 2 years values (with 95% CIs) for each treatment, and the between-treatment difference in changes from baseline to 2 years (with 95% CI and a P-value for the null hypothesis of no difference).
2. The **KOOS Pain** subscore will be analyzed with a linear mixed model with treatment, time point (baseline, 1 year, 2 years), and treatment x time point interaction as fixed effects. A random intercept will be used. Based on the fitted model, we will estimate the mean baseline, 1 year, and 2 years values (with 95% CIs) for each treatment, and the between-treatment difference in changes from baseline to 2 years (with 95% CI and a P-value for the null hypothesis of no difference).
3. The **KOOS Activities of Daily Living** subscore will be analysed with a linear mixed model with treatment, time point (baseline, 1 year, 2 years), and treatment x time point interaction as fixed effects. A random intercept will be used. Based on the fitted model, we will estimate the mean baseline, 1 year, and 2 years values (with 95% CIs) for each treatment, and the between-treatment difference in changes from baseline to 2 years (with 95% CI and a P-value for the null hypothesis of no difference).

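### The blinded/unblinded subgroup model states no blinded or blinded-by-time term and reads two P-values as effect modification, although neither term as written isolates it

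*SAP*

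**What the plan says.** SAP section 10.3.1 gives the primary model as a "linear mixed model with treatment, time point (baseline, 1 year, 2 years), and treatment x time point interaction as fixed effects", and adds: "A random intercept will be used". Its target is the between-arm difference in change in KOOS QoL from baseline to two years.

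Section 10.3.3 defines the subgroups by enrolment order: "The subgroup would contain patients with randomization number 1-61 versus 62-120". The model is obtained by "adding an interaction term between blinded and treatment and an interaction term between blinded and (treatment x time) to the linear mixed model". The reading rule follows: "The P-values for these interaction terms will indicate whether any difference in treatment effects exists between blinded and not blinded patients".

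The subgroups exist because blinding changed during enrolment. Section 9.2 says: "Initially, the trial participants were not intentionally blinded for the intervention, but the outcome assessor was blinded". Participants from number 62 onward were then blinded. Section 3.2 records another change during inclusion: "From March 1st, 2013 until end of inclusion, the site of intervention was changed to Martina Hansens Hospital". Section 12 adds a new recruiting hospital and a changed graft-size criterion.

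**The concern.** A test of whether blinding modifies the treatment effect needs a model in which the two halves of the trial may differ in level and in course over time, equally in both arms. The blinded and blinded-by-time terms do this. Section 10.3.3 names neither, although section 10.3.1 lists the lower-order terms of the primary model one by one.

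There is a second problem. Baseline is one of the outcome visits. With baseline as the reference, blinded-by-treatment compares the arms before surgery. It cannot show a difference in treatment effect, yet its P-value is to be read that way.

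This is the only planned analysis of whether the change in blinding affected the primary result. A false signal could be taken as bias from unblinded patients, and the stated P-values could not correct that reading.

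**Working it through.** **The plan's own figure.** The SAP gives no figure for the subgroup test. The sample size in section 8 supplies the SD and reproduces: n = 2 × (1.96 + 0.84)² × 15² / 8² = 55.2, so 56 per arm. With 5% drop-out, 56 / 0.95 = 58.9, so 59; the plan sets 60.

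**What the literal model estimates.** Let T = 1 for one arm, B = 1 for patients 62-120, and d2 = 1 at two years. With 0/1 products and the one-year terms left out for brevity, the mean is

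b0 + b1·T + b2·d2 + b3·T·d2 + g·B·T + h·B·T·d2.

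- For T = 0, B drops out. The reference arm has the same means in both halves.
- For T = 1, g is the blinded-minus-unblinded difference at baseline, and h is the blinded-minus-unblinded difference in two-year change.
- The intended quantity is h minus the same difference in the reference arm. If both arms shift by d points in two-year change, h = d and the true interaction is 0, so the whole shift appears as effect modification.
- With the other arm as reference, h is again d but is credited to the opposite technique. Section 10.4 codes the arms anonymously as treatment 1 and treatment 2 and fixes no reference.

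**Standard errors.** Inputs: SD 15 (section 8); 61 and 59 patients in blocks of ten (sections 10.3.3 and 9.1), hence about 30 per cell; complete data. The within-patient correlation r is not in the SAP and is taken as 0.3 to 0.7. The SD of change is 15 × √(2(1 − r)), which is 15 at r = 0.5.

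- Literal h: 15 × √(2/30) = 3.87 at r = 0.5.
- Full-model interaction: 15 × √(4/30) = 5.48 at r = 0.5.

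**Rejection by the literal two-year three-way test, no true interaction.** The rate is Φ(d/SE − 1.96) + Φ(−d/SE − 1.96).

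| Common shift d in change (assumed) | r = 0.3 (SE 4.58) | r = 0.5 (SE 3.87) | r = 0.7 (SE 3.00) |
|---|---|---|---|
| 0 | 5% | 5% | 5% |
| 2 points | 7% | 8% | 10% |
| 5 points | 19% | 25% | 38% |
| 8 points | 42% | 54% | 76% |

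With blinded and blinded-by-time added, the expected coefficient is 0 and the rate is 5% in every cell.

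**Simulation check** (1,000 trials per scenario, REML, r = 0.3 and 0.5, half of any shift in change present at one year, all time levels of the three-way term tested jointly):

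- Shift of 4 or 8 points in two-year change: the three-way term is significant in 12-13% or 31-44% with 0/1 coding, and in 14-17% or 49-65% with factor coding. Under factor coding the terms expand to 2 and 4 degrees of freedom and absorb the omitted blinded effects.
- Constant level shift of 4 or 8 points: blinded-by-treatment is significant in 17-19% or 52-53% (0/1), and in 23-27% or 72-75% (factor).
- Adding the blinded main effect alone leaves the three-way test at 12-13% and 31-44%.
- Full model: each test rejects in about 4-7%. The chance that at least one of the two P-values is below 0.05 is still about 8-11%, because no rule says which one decides.

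**The case against.** The best defence is that section 10.3.3 names only the terms to be tested, and that any statistician would include the lower-order terms. The section does not exclude them. This may be what was meant, but section 10.3.1 spells out its lower-order terms and section 10.3.3 builds on that list. The defence also leaves the reading rule wrong: in the full model, blinded-by-treatment at baseline is still a preoperative difference.

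A reader might infer that a period effect is to be expected, or that blinding coincides with the hospital move. The SAP supports neither. It does not date the enrolment of patient 62, reports no drift in KOOS QoL, and says in section 12 that the surgeon continued under unchanged conditions with the same equipment. Without a period difference the literal tests reject at about 5-6% each.

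A reader might also take the constrained reference arm and the smaller standard error as general. They belong to 0/1 coding; which arm is constrained depends on the reference chosen. Factor coding fails differently, by mixing the blinded effects into the tests.

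Finally, low power is not part of this point. With standard error 5.48, power for an 8-point difference in effects is about 31%, but that is a limit of a subgroup test at this sample size, and the extra terms do not cure it.

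**Conclusion.** The point stands as a should-fix. As written, neither added term isolates a difference in treatment effect between blinded and unblinded patients, and the rule for reading the two P-values is wrong even if the lower-order terms are implied.

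The size is conditional. Under 0/1 coding, the false-positive rate of the two-year three-way test is about 7-10% for a 2-point common shift in change, 19-38% for 5 points and 42-76% for 8 points, against about 5% in the full model. The shifts and the correlation are assumptions; 8 points equals the plan's whole minimal important change. A shift is plausible because the subgroups follow enrolment order while the site of surgery, the recruiting hospitals and the graft-size criterion changed during inclusion. It is not established.

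It would be wrong to conclude that the primary result is compromised. The primary model and contrast in section 10.3.1 are untouched.

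**What to change.** In section 10.3.3:

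1. State the fixed effects in full: treatment, time point, blinded, all three two-way interactions and the three-way interaction, with the random intercept kept.
2. Base the subgroup inference only on the blinded-by-treatment-by-(two years versus baseline) contrast, which matches the primary estimand. Remove the statement that the P-value of blinded-by-treatment shows a difference in treatment effects.
3. Report the treatment effect with 95% CI in each subgroup, and the difference between them with its 95% CI.
4. Note that blinding is confounded with calendar time and possibly with site, which no added term can separate.

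The cost is a few lines of wording and two model terms (blinded and blinded-by-time). The interaction interval becomes wider: a standard error of about 5.5 rather than 3.9 points at correlation 0.5. That width is the real uncertainty of the intended contrast. No new data are needed.

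### Section 10.3.3 judges the influence of blinding by interaction P-values alone, with about 30% power for an 8-point difference and no interval explicitly planned to show that imprecision

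*SAP*

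**What the plan says.** Section 10.3.3 plans one subgroup analysis of the primary outcome, by blinding status: "The subgroup would contain patients with randomization number 1-61 versus 62-120". That gives 61 unblinded and 59 blinded patients. A blinded-by-treatment term and a blinded-by-(treatment x time) term are added to the linear mixed model. The section then says how the result is to be read: "The P-values for these interaction terms will indicate whether any difference in treatment effects exists between blinded and not blinded patients". It mentions no estimate, confidence interval, significance level or power for this comparison.

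Section 10.3.1, by contrast, requires the between-treatment difference in change to two years with a 95% CI and a P-value for the primary analysis.

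Section 8 sizes the trial for the overall comparison only: "A minimal important change (MIC) in QoL of 8 points, has been considered sufficient [23", with "a standard deviation of 15 points" and "assuming a two-sided significance-level of 0.05". From these inputs, "the sample size was calculated to be 56 patients in each treatment group". This was raised to 60 per arm, 120 in total, for 5% drop-out.

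Section 12, under the blinding heading, explains that patients were blinded from number 62 onwards to keep them from unintentionally biasing the results.

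**The concern.** KOOS QoL is reported by the patient, and about half the patients were not deliberately blinded. The SAP itself treats this as a possible source of bias, and section 10.3.3 is the only analysis in the SAP that addresses it.

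The trial is sized to detect 8 points between two arms of about 60. A difference between two subgroup effects, each resting on about 30 patients per arm, has roughly twice the standard error. A P-value above 0.05 is then the more likely result even if unblinding shifted the treatment effect by as much as the trial's own minimal important change. With only a P-value, a reader cannot tell a result that rules out a relevant difference from one that is merely imprecise.

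The stake is how far the pooled primary estimate can be trusted. As an illustration, assume no true effect and an 8-point apparent effect created by unblinding in patients 1-61. The pooled estimate would move by 8 x 61/120 = 4.1 points, about 1.5 of its standard errors (2.74), and the interaction test would still usually be non-significant.

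**Working it through.** **Inputs.** From section 8: difference 8 points, SD 15, two-sided alpha 0.05, power 80%, equal allocation. From section 10.3.3: 61 and 59 patients. From section 9.1: blocks of ten at 1:1, so the arms are about equal within each subgroup. Two inputs are assumptions: that the difference in effects between subgroups is 8 points, and that the interaction is tested at 0.05. The SAP gives neither.

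**1. The SAP's own figure.** n per arm = 2 x [15 x (1.960 + 0.842) / 8]^2 = 55.2, rounded up to 56. This reproduces. 56 / 0.95 = 58.9, so 59, and the SAP uses 60.

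**2. Main effect, 60 per arm.** SE = 15 x sqrt(2/60) = 2.74.

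**3. Two-year interaction contrast, SD 15 taken as the SD of change.** SE = SD x sqrt(sum of 1/n over the four treatment-by-blinding cells). Power = Phi(8/SE - 1.96) + Phi(-8/SE - 1.96). The difference detectable with 80% power is 2.80 x SE.

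| | Cell sizes | SE | 95% half-width | Power for 8 points | Miss rate | Detectable at 80% power |
|---|---|---|---|---|---|---|
| All 120 patients | 30.5, 30.5, 29.5, 29.5 | 5.48 | 10.7 | 31% | 69% | 15.3 |
| 112 patients (2 x 56) | 28.5, 28.5, 27.5, 27.5 | 5.67 | 11.1 | 29% | 71% | 15.9 |

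About 444 patients in total would be needed for 80% power at 8 points.

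**4. If 15 is the SD at a single time point.** Section 8 does not say which it is. The SD of change is then 15 x sqrt(2(1 - rho)), with rho the assumed correlation between baseline and two years. Miss rates are for 120 and 112 patients.

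| rho (assumed) | SD of change | Miss rate for 8 points |
|---|---|---|
| 0.3 | 17.75 | 76-78% |
| 0.5 | 15.0 | 69-71% |
| 0.6 | 13.4 | 63-65% |
| 0.7 | 11.6 | 53-56% |
| 0.8 | 9.5 | 36-39% |

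**5. Which P-value is read.** The section speaks of P-values in the plural, and the three-way term spans two follow-up times. The figures here take SD 15 per time point, rho 0.5 and all 120 patients.

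- A joint 2-df test of the three-way term has 24-31% power, depending on the one-year effect.
- If any single significant coefficient counts, the chance of a flag is about 45-48% for an 8-point shift at both follow-ups, and about 34-36% for a shift at two years only. The lower figure in each pair counts the two three-way coefficients. The higher adds the blinded-by-treatment term.

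With baseline as the reference time, the blinded-by-treatment term describes a baseline imbalance and not a treatment effect. Only the two-year three-way contrast answers the question, and the SAP does not single it out.

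**6. Precision within each subgroup, SD of change 15.** Blinded: SE = 15 x sqrt(4/59) = 3.91, half-width 7.7 points. Unblinded: SE = 15 x sqrt(4/61) = 3.84, half-width 7.5 points.

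**The case against.** **The SAP sets no decision rule.** It gives no alpha for the interaction, does not say that a non-significant P means no difference, and ties no consequence for the pooled analysis to the result. This stands. A reader might infer that the SAP lets the P-value decide the matter, or that a non-significant result would clear the unblinded half. The text supports neither. It says only that the P-values indicate whether a difference exists.

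**Estimates may be implied.** The section opens by announcing a separate analysis of the primary outcome and extends a model for which section 10.3.1 already requires an estimate with CI. On a generous reading those outputs carry over. This stands in part: it would be wrong to say the SAP excludes them. But where section 10.3.3 states what will answer the question, it names P-values alone.

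**The miss rate is not one fixed number.** It depends on what the SD of 15 describes, on the correlation, and on which P-value is read. This also stands. A claim that the test misses 70% or more would hold only under some of these assumptions.

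**The 8-point benchmark is borrowed.** It is the minimal important change from section 8, and nothing in the SAP says unblinding would shift the between-arm difference by that much. It is used here only as a yardstick. The CI half-width does not depend on it.

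**Low interaction power is common, and a prespecified interaction test on a single factor is accepted method.** Agreed. The test itself is sound. The point concerns what is reported beside it.

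**Conclusion.** The point holds as one of reporting and interpretation. Section 10.3.3 rests the question of whether blinding altered the treatment effect on interaction P-values, without explicitly planning the interaction estimate or the subgroup effects with intervals.

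If 15 is the SD of change, the two-year contrast has a half-width of about 10.7 points, wider than the 8 points the trial treats as important, and about 30% power for a difference of that size (miss rate about 70%). If 15 is a single-time-point SD and the correlation is assumed to be 0.6-0.7, the miss rate is about 53-65%. It falls below one half only at higher correlations, such as 0.8. All these figures are for the single two-year contrast and assume a test at 0.05.

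A non-significant P would thus be weak evidence that unblinding had no effect, and nothing explicitly planned would show the reader how weak. The primary analysis itself is not affected.

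**What to change.** Replace the last sentence of section 10.3.3 with wording such as:

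> From the extended mixed model, the between-treatment difference in change in KOOS QoL from baseline to two years will be reported with a 95% CI for patients 1-61 and for patients 62-120. The two-year blinded x treatment x time contrast will be reported with a 95% CI and P-value. A non-significant interaction will not be taken as evidence that the treatment effects are equal.

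Naming the two-year contrast also settles which of the several P-values is meant. The blinded-only estimate should be presented as imprecise (half-width about 7.7 points at SD 15), so that it is not over-read in turn.

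The cost is a change of wording and a few contrasts from a model already planned, with no new data. The downside is that the SAP gives up a yes/no statement on the influence of blinding.
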